### **Sample Size Justification**

Power Analyses from Research Plan:

(Aim 1) To test the hypothesis for Aim 1, a paired-sample diagnostic analysis (estimated sensitivities/specificities) for each screening measure relative to the criterion standard, Level 1 PSG) was

performed using the same sample of patients. Prevalence of sleep apnea (as determined by Level 1 PSG) was conservatively estimated to be 30% using investigators' published reports of 37-39% prevalence in acute rehabilitation TBI samples. A two-sided McNemar's test, assuming a significance level of  $\alpha = 0.05$ , will have at least 80% power to detect a difference in sensitivities of 20% between screening measures for a sample size of 237. The power of the test will increase if the prevalence is higher than 30% (e.g., a prevalence of 35% would yield 87% power with 237 subjects and only require 203 subjects for 80% power). Furthermore, a sample size of 237 will have at least 80% power to detect a difference of 20% in sensitivities between screening measures in detecting sleep apnea.

(Aim 2) To test the non-inferiority hypothesis of the portable device for diagnosing sleep apnea, the non-inferiority of SE and SP (relative to SEH = 0.9 and SPH = 0.6, each within  $\Delta = 0.1$ ) were jointly tested at the significance level of  $\alpha=0.05$  by estimating the cross-product of two one-sided  $1-\alpha^*$  confidence intervals; SEH and SPH were selected a priori and were considered sufficiently large to obviate the need Level 1 PSG. For the purposes of the clinical trial, the study was powered to demonstrate non-inferiority of Level 3 sleep studies relative to fixed values of sensitivity (SE) and specificity (SP). Minimum sample sizes of 83 and 153 patients achieved at least 80% power to detect non-inferiority of SE to 90% and SP to 60% with a non-inferiority limit of  $\Delta = 0.1$ , using one-sided exact tests each at a 5% level of significance. In total, 214 subjects were available for analysis which yields 83.9% and 98.8% power, respectively, when testing the non-inferiority of SE and SP each at a 2.53% level of significance and maintaining a 5% level of significance when testing SE and SP jointly.

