Using individual significance levels of  $\alpha_{SE} = \alpha_{SP} = \alpha^* = 0.0253$  ensures that the overall significance region of the joint test of both SE and SP simultaneously remains no greater than  $\alpha = 0.05$ . If the lower confidence limits (LCL) from both  $1 - \alpha^* = 94.9\%$  confidence intervals are strictly above 0.8 for SE and 0.5 for SP, then a claim of non-inferiority of the portable diagnostic test would be established. Analyses were conducted for each AHI cutoff score (Total AHI  $\geq 5$ ,  $\geq 15$ , and  $\geq 30$ ) for the overall sample and by subgroups. The non-inferiority thresholds were chosen based on a prior systematic review showing estimates of SEs and SP for AHI  $\geq 5$  were 0.96 (95% CI = 0.90, 0.98) and 0.76 (95% CI = 0.63, 0.85), respectively, across varying OSA prevalence rates. Based on the lower bounds of these 95% confidence intervals (rounded to the nearest 10th), 90% SE and 60% SP with a delta of 0.1 were selected for declaration of non-inferiority.

3. Pepe MS. *The statistical evaluation of medical tests for classification and prediction*. 2003; Oxford University Press, New York.

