(Aim 2: Hypothesis 2.1): *Level 3 portable polysomnography with greater consumer accessibility will be equivalent (non-inferior) to the less accessible Level 1 polysomnography in determining presence of sleep apnea in TBI patients undergoing inpatient rehabilitation.* Justification of Assumptions/Power Estimate: To test hypothesis 2.1, the sensitivity (SE) and specificity (SP) of Level 3 PSG (compared to Level 1 PSG, the reference gold standard) will each be estimated and compared to fixed hypothesized rates of SE and SP considered sufficiently large enough to potentially obviate the need for Level 1 PSG. Based on a review of the literature and consensus among the investigators in this study, SE and SP no worse (non-inferior) to 90% and 60%, respectively, are considered sufficiently large enough. To test for non-inferiority of the SE to 90% and the SP to 60%, a non-inferiority threshold of $\Delta = 0.1$ is assumed for both measures. A sample size of at least 83 patients is necessary to achieve a minimum of 80% power to test the non-inferiority of the SE to 90% (assuming $\Delta = 0.1$ and $\alpha = 0.05$). A sample size of at least 153 patients is necessary for a minimum of 80% power to test the non-inferiority of the SP to 60% (assuming $\Delta = 0.1$ and $\alpha = 0.05$). Thus, a total of 153 subjects is required to sufficiently power both non-inferiority hypotheses. Analytic Plan: To test hypothesis 2.1, the sensitivity (SE) and specificity (SP) of Level 3 PSG (compared to Level 1 PSG, the reference gold standard) will each be estimated and compared to fixed hypothesized rates of SE and SP of 90% and 60%, respectively, considered sufficiently large enough. Level 1 PSG (reference) diagnosis of sleep apnea will be made based on $AHI \geq 5$. Level 3 PSG (test) diagnosis will be made based $AHI \geq 5$. A cross-tabulation of Level 3 PSG (positive/negative) versus Level 1 PSG (positive/negative) will be constructed and standard measures of diagnostic accuracy will be estimated along with 95% confidence intervals (i.e., sensitivity, specificity, positive and negative predictive values, and diagnostic accuracy). To test for non-inferiority of the SE to 90% and the SP to 60%, a non-inferiority threshold of 0.1 is assumed. If the lower bound on the 95% confidence interval for SE is strictly above 80% and the lower bound on the confidence interval for SP is strictly above 50% then non-inferiority of Level 3 PSG (compared to Level 3 PSG) can be established. All analyses will be performed using SAS v.9.4 (SAS Institute Inc., Cary, NC).

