
Exploratory Aim 1 (HTE analyses): While an analysis of heterogeneity of treatment effects does not apply to the current study design, an important question to answer is whether the diagnosis of sleep apnea can be impacted by the presence of post-traumatic amnesia (PTA). The confusion and behavioral dysregulation associated with PTA could potentially reduce the person's ability to tolerate the procedures. While the lead site has successfully obtained PSG with EEG with persons experiencing PTA, this was a single site study with a select subject population (veterans who primarily experienced blast-induced TBI). The current study will allow for an assessment of differences in diagnostic accuracy with persons who are currently experiencing PTA in comparison to those who have cleared PTA. PTA will be operationalized based on the criterion used by the TBIMS consortium (obtaining an Orientation Log or

Galveston Orientation Amnesia Test scores in target range or consistent, repeated demonstration of orientation in medical record review). Analytical Plan: To address exploratory aim 1 regarding the heterogeneity of the screening and diagnostic accuracy across relevant sub-groups, the methods detailed for the primary aims will be replicated for the subgroups of injury severity (GCS), cognitive status (PTA), motor confounds (spasticity and hemiparesis), and limb placement. As these are exploratory aims and the study is not powered to test for differences or non-inferiority within each sub-group, focus will be on comparing the effect size of proportions (Cohen's h) among the subgroups. Values for h of 0.2, 0.5, and 0.8 are typically considered to be small, medium, and large differences, respectively. All analyses will be performed using SAS v.9.4 (SAS Institute Inc., Cary, NC).

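### The Protocol's 5% error limit covers one joint sensitivity and specificity test, but the Aim 2 analyses are run at three AHI cut-offs and by subgroups, with none named as the basis of the claim

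*Protocol*

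**What the plan says.** **Protocol, Statistical Analysis Plan, Aim 2.** Testing SE and SP at 0.0253 each "ensures that the overall significance region of the joint test of both SE and SP simultaneously remains no greater than" 0.05. The decision rule follows: if both lower confidence limits "are strictly above 0.8 for SE and 0.5 for SP, then a claim of non-inferiority of the portable diagnostic test would be established". The text goes on: "Analyses were conducted for each AHI cutoff score", listing AHI ≥ 5, ≥ 15 and ≥ 30, "for the overall sample and by subgroups". On the targets: "The non-inferiority thresholds were chosen based on a prior systematic review showing estimates of SEs and SP for AHI" ≥ 5. The lower ends of those two confidence intervals gave 0.9 for SE and 0.6 for SP.

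**Protocol, Sample Size Justification.** Power is given for one pair of tests in 214 patients, "when testing the non-inferiority of SE and SP each at a 2.53% level of significance and maintaining a 5% level of significance" for the pair.

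**SAP, Aim 2 (Hypothesis 2.1).** "Level 1 PSG (reference) diagnosis of sleep apnea will be made based on" AHI ≥ 5. The portable test uses the same cut-off, and there is a single non-inferiority conclusion.

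**SAP, Exploratory Aim 1.** The primary methods are repeated in subgroups (GCS, post-traumatic amnesia, spasticity and hemiparesis, limb placement), but "the study is not powered to test for differences or non-inferiority within each sub-group". The focus there is on Cohen's h.

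**The concern.** The 5% guarantee attaches to one joint test. The sentence after the decision rule spreads the analysis over three cut-offs and an uncounted set of subgroups, and does not say which result decides. If the portable test passed at one cut-off and failed at another, the Protocol does not tell the reader whether Aim 2 succeeded. The claim matters because it is meant to show that Level 1 polysomnography may be unnecessary.

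The SAP does settle this, with one cut-off and exploratory subgroups, so the two documents allow different claims from the same data.

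Two further issues follow. The targets were derived from AHI ≥ 5 estimates, and neither document argues that they suit AHI ≥ 15 or ≥ 30. And if an analysis has few reference-positive patients, failing the rule may reflect the count and say nothing about the device.

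**Working it through.** **Inputs.** Per-measure level 0.0253, null values 0.8 (SE) and 0.5 (SP), N = 214, three cut-offs (Protocol, Aim 2 and Sample Size Justification). Prevalence 30% (Sample Size Justification, Aim 1). No prevalence is given for AHI ≥ 15 or ≥ 30, and no subgroup sizes. I read the 94.9% interval as two-sided, so that its lower limit is one-sided at 2.53% (1 − 2 × 0.0253 = 0.949).

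**1. The stated 5%.** 1 − (1 − 0.0253)² = 0.04996, which reproduces 0.05 for one SE and SP pair.

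**2. Error of one joint claim.** Both measures must pass, so a false claim has probability at most 0.0253. The worst case is one measure on its bound and the other certain to pass.

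**3. Three overall cut-offs, ceiling.** Sum bound: 3 × 0.0253 = 0.0759, or 7.6%. If independent: 1 − (1 − 0.0253)³ = 0.074.

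**4. Three overall cut-offs, likely values.** Exact tests fall short of their nominal level, and nested cut-offs share patients. The chance of at least one false pass was simulated (200,000 runs) with one measure on its bound at every cut-off and the other taken to pass. Prevalences at AHI ≥ 5 / ≥ 15 / ≥ 30 are assumptions.

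| Assumed prevalence | Positives of 214 | SE on bound: errors shared / independent | SP on bound: errors shared / independent |
|---|---|---|---|
| 30 / 15 / 10% | 64 / 32 / 21 | 2.8% / 3.5% | 3.3% / 6.3% |
| 60 / 30 / 15% | 128 / 64 / 32 | 3.5% / 4.4% | 4.1% / 6.2% |
| 70 / 40 / 20% | 150 / 86 / 43 | 4.3% / 5.4% | 4.1% / 5.9% |

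The range is about 3% to 6%.

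**5. Smallest workable count for SE.** With n reference-positives all detected, the exact one-sided p-value is 0.8ⁿ.
- n = 16: 0.8¹⁶ = 0.0281, above 0.0253. The lower limit is 0.0253^(1/16) = 0.795, which fails.
- n = 17: 0.8¹⁷ = 0.0225. The lower limit is 0.0253^(1/17) = 0.806, which passes.

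So at least 17 positives are needed. In the overall sample that is 17/214 = 7.9%. In a subgroup of 56 at 30% prevalence the expected count is 0.30 × 56 = 16.8, just short. Wilson limits would need 16. The Aim 2 analysis text names no interval method; exact tests appear only in the sample-size text.

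**6. Power with few positives.** With 32 positives (15% of 214), the exact rule requires 31 detected. Power is 16% at true SE 0.90, 63% at 0.96 (the review estimate cited in the Protocol) and 87% at 0.98.

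**The case against.** The strongest reply is that the SAP already deals with this. It fixes AHI ≥ 5 for both tests, calls the subgroups exploratory and unpowered, and turns to effect sizes there. The Protocol speaks of a claim in the singular and then of analyses; it does not say that a claim is declared for each. The excess over the three overall cut-offs is also small, and most of the simulated values are at or below 5%. The SAP further rests the targets on investigator consensus about what would be good enough, so they do have some basis beyond the review. All of this limits the point. It does not remove it, because the Protocol carries none of the SAP's restrictions, and the consensus is applied in the SAP at AHI ≥ 5.

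Three stronger readings are tempting, and the documents do not support them.

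- **Error above 50%.** A reader might count 10 subgroup strata plus the overall sample at three cut-offs, 33 claims, and get 1 − (1 − 0.0253)³³ = 57%. The number of strata is a guess, the same patients recur across subgroup factors and cut-offs, and small strata fall well short of 2.53%. The exact size of the SE test is 0.92% with 21 positives, 0.71% with 32, and zero below 17.
- **Some tests cannot succeed.** This requires fewer than 17 positives (exact limits). The documents neither show nor exclude it, and they give no counts. A low power such as 16% likewise holds only at true SE 0.90.
- **The rule is applied in every subgroup.** The Protocol says only that analyses were done by subgroups, and names none under Aim 2.

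**Conclusion.** The point holds as a conflict between Protocol and SAP over what may be claimed. The 5% limit belongs to one joint test, and the Protocol neither names that test among its three cut-offs and subgroups nor adjusts for the others.

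If each overall cut-off can carry a claim, the error ceiling is 7.6%. Likely values are about 3% to 6%, resting on assumed prevalences and exact tests. Reading subgroup results as claims would raise this by an amount that cannot be calculated from the documents. The 0.9 and 0.6 targets lack a cut-off-specific basis at AHI ≥ 15 and ≥ 30, whatever view is taken of multiplicity. The minimum of 17 positives is exact arithmetic for exact limits, but whether any analysis falls below it is unknown. The demonstrated inflation is modest; the main defect is that the deciding result is not identified.

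**What to change.** In the Aim 2 paragraph of the Protocol's Statistical Analysis Plan, state that the non-inferiority claim rests on AHI ≥ 5 in the overall sample, as in the SAP. Report AHI ≥ 15, AHI ≥ 30 and all subgroups as descriptive results, with the numbers of reference-positive and reference-negative patients, SE and SP with confidence intervals, and no declaration of non-inferiority. The counts let a reader see where a wide interval reflects small numbers.

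This changes wording only and needs no new data. The downside is that no confirmatory claim is made for moderate or severe apnea or for any subgroup. Since the Protocol text was written after the study finished, the edit cannot by itself create pre-specification; it aligns the Protocol with the single test in the SAP.

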#### Assessment of Safety

Potential adverse events were monitored by local study teams under oversight by local institutional review boards. Potential risks associated with this type of observational sleep research are minimal. The sleep assessment procedures employed in this study are commonly used in clinical sleep evaluations. Risk of physical harm or injury is unlikely given non-invasive nature of ACG and PSG. The Actiwatches® (ACG) wrist bands could be physically or emotionally distracting. The multiple monitoring devices required for (PSG) may be uncomfortable either physically or emotionally. The placement of breathing bands could result in contact dermatitis. Some of the questions asked during the assessment periods might be deemed personal or sensitive and make the participant feel uncomfortable. There was the risk that the study assessments will discover a medical condition previously unknown to the participant such as the diagnosis of sleep apnea or another sleep disorder. There was also a chance that a participant could experience medical distress or a medical emergency unrelated to the study during the course of an assessment. There was a remote chance that an outside party may discover a participant's identity and participation in the study. No risk to study personnel was anticipated.

#### Pregnancy

If a female participant was pregnant during the trial, no alteration of study procedures was indicated.

#### Data Safety Monitoring

A data safety monitoring board was not required.

#### Data Monitoring

The PI and Site PIs were responsible for study conduct and compliance with the overall protocol, good clinical practice (GCP), applicable regulatory requirements, and that the data recorded were valid. To achieve this objective, the study team continuously monitored the enrollment and completion of participants in the trial on a weekly basis using live-reports and bi-weekly, multi-center meetings.

#### Data Handling and Record Keeping

Procedures for the current study were carefully documented in a Manual of Procedures, and adherence to the procedures will be regularly monitored by the lead site. Standard procedures as recommended by the American Association of Sleep Technologists were followed for performing the PSGs, with the exception that the studies will be conducted on the rehabilitation units rather than in a sleep lab. Likewise, standard procedures for administering the screening measures and other instruments were also followed.

### **Institutional Review Board**

All sites received Institutional Review Board approval to conduct the study.

### **Consent Process**

*Summary of Existing Currently Funded TBIMS Study Procedures.* Eligibility is determined in consecutive admissions to inpatient brain injury rehabilitation by TBIMS staff already in place at each site. (Consent) TBIMS procedures in place commonly identify eligible candidates prior to admission with consent obtained during rehabilitation. TBIMS procedures in place at each site track subject eligibility and reason for exclusion into the TBIMS. These data are submitted quarterly to the TBIMS National Data Center for quality control purposes and subject tracking to meet data quality standards and input into Standards for Reports of Diagnostic Accuracy (STARD) diagrams. Consent and eligibility were tracked for this project using the same procedures already in place.

### **Protocol Deviation**

Protocol deviations occur when noncompliance with the clinical trial or GCP requirements. No protocol deviations occurred during the trial.

### **Laws and Regulation**

The clinical study was completed in compliance with all national laws and regulations of the United States. The trial was registered on [www.clinicaltrials.gov](http://www.clinicaltrials.gov).

### **Publication and Data Sharing Policy**

In accordance with Standard Operating Procedures in place for each TBI Model System and implemented by the TBIMS National Data Center (Infrastructure leveraged for this project), C-SAS unique data elements will be archived at the lead study site (Tampa VA) and made available for future analyses and dissemination following TBIMS established procedures. Both internal and external investigators will be able to request the data following completion of a Notification Form and Data Use Agreement that was developed by the TBIMS National Data Center. Syllabus and protocol materials will be made available online similar to other data elements collected in the TBI Model Systems (<https://www.tbindsc.org/Syllabus.aspx>). The Internal and External Notifications for Data Use and Data Use Agreement Policies will remain a method for ongoing continued access for both funded TBI Model System investigators (Internal Requests) and other scientists (External Requests). Finally, all manuscripts describing the study's procedures and protocols will be submitted to PubMed Central to maximize data sharing.

Comparison of Sleep Apnea Assessment Strategies to Maximize TBI Rehabilitation Participation and Outcome (C-SAS)

NCT03033901

Document Date: September 16, 2020

Title: **Comparison of Sleep Apnea Assessment Strategies to Maximize TBI Rehabilitation Participation and Outcome (C-SAS)**

Primary Investigator:

[name]., FACRM, FNAN

Mental Health and Behavioral Sciences, Defense and Veterans Brain Injury Center at James A. Haley Veterans' Hospital, Morsani College of Medicine, Division of Pulmonary and Sleep Medicine, University of South Florida, Tampa, FL

[contact]

[contact]

Sponsor:

Patient Centered Outcomes Research Institute

[name]

[name]

[contact]

[contact]

STUDY SUMMARY

Title	Comparison of Sleep Apnea Assessment Strategies to Maximize TBI Rehabilitation Participation and Outcome (C-SAS)
Methodology	Prospective, diagnostic clinical trial
Study Duration	Study recruitment was initiated on 05/2017 and completion of all participants in the protocol occurred on 02/2019.
Study Centers	Potential participants were consecutive patients enrolled in the TBI Model Systems (TBIMS) at six sites (Tampa, FL [James A. Haley Veterans Hospital]; Seattle, WA [University of Washington]; Dallas, TX [Baylor Scott & White Rehabilitation]; Columbus, OH [Ohio State University]; Denver, CO [Craig Hospital]; and Philadelphia, PA [Moss Rehabilitation Institute]).
Objectives	
Aim 1: For individuals with TBI, determine comparative effectiveness of AASM endorsed patient-reported screening tools and objective actigraphy to identify those at high risk of sleep apnea as diagnosed through Level 1 Diagnostic Polysomnography.
 
Aim 2: Determine the diagnostic accuracy (non-inferiority of Level 3 portable diagnostic testing in determining presence of sleep apnea in patients with acute TBI patients in the rehabilitation setting.

Number of Subjects	
Aim 1: 248
 
Aim 2: 214

Diagnosis and Main Inclusion Criteria	
Inclusion Criteria:
 
 *Damage to brain tissue caused by an external mechanical force *Alteration of consciousness > 24 hours, or loss of consciousness > 30 minutes, or Glasgow Coma Scale (GCS) score in the Emergency Department of 3-12, or intracranial abnormalities on imaging regardless of GCS *Admission to inpatient rehabilitation *Minimum age 16 years at civilian sites and 18 years at the VA site *Consent to participate by person with brain injury (if able), family member or legally authorized representative into the TBI Model System lifetime study. This criterion was relaxed in Study Month 11.

	
Exclusion Criteria:
 
 *Habitual sleep duration > 2 hours/night for two (2) consecutive nights not being established prior to PSG *Presence of a physical deformity precluding sensitivity of PSG instrumentation (i.e. full body cast, PSG that could not be removed prior to PSG) *Medical instability as determined by the treating physician (i.e. agitation, acute illness) *Infeasibility of tracheostomy placement with decannulation or overnight capping during rehabilitation

Study Product
	
Aim1: Subjects will complete paper and pencil screening tests (STOPBang, Berlin, MAPI), actigraphy, and Level 1 Diagnostic Polysomnography.
 
Aim 2: Subjects recruited will undergo simultaneous administration of Level 1 Diagnostic Polysomnography and Level 3 Portable Diagnostic tests.

Statistical Methodology
	
Aim 1: Area under the curve (AUC) of screening tools predicting sleep apnea status and severity.
 
Aim2: Non-inferiority of Level 3 portable diagnostic tests to the criterion standard, Level 1 Polysomnography.

Statistical and Power Considerations

Data Quality & Management. During its' 25-year tenure, the TBIMS has developed extensive quality control procedures to minimize missing data (quarterly missing data reports, data entry filters/feedback), minimize attrition (follow-up strategy standards with monitored adherence) and enhance data capture (periodic on-site audits) which will be part of the infrastructure utilized in this study assuring robust capture of needed covariates and outcomes. Study sites collaborating on sleep research meet monthly via teleconference to review procedural issues and review quarterly reports as part of the TBIMS Sleep Special Interest Group. Existing bi-annual meetings in Washington DC will be utilized to discuss data collection, quality, analyses, and dissemination activities throughout this grant cycle. A mandatory 2-day training will occur with site PI and PSG technician in Tampa, Florida to standardize assessment protocols. Study teams will meet weekly in the first three months to monitor progress with IRB activities and hiring of new personnel. Biweekly telephone calls will occur the following three months and transition to monthly calls to discuss study progress. **(Data Management).** The database will be developed by the TBIMS National Data and Statistical Center at Craig Hospital which has the existing infrastructure and IRB-approved clearances to accept both civilian and VA data for the TBIMS program. Only registered TBIMS users will be assigned a password to access the database for online data entry. Once data collection is complete, study information will be entered into a password protected database accessible via secured-internet connection. Study databases will be automatically linked to existing TBIMS databases with demographic, injury severity, and rehabilitation outcome data collected as part of the TBIMS infrastructure. All data will be de-identified to protect the privacy of participants. Each subject will retain the original TBIMS ID number to allow for merging of the data between the C-SAS and TBIMS data elements. Project investigators will audit data entry prior to final submission as part of routine TBIMS study procedures. To facilitate scoring and interpretation of the PSG studies, the PSG data from all sites will be transferred from the National Data Center to the Tampa VA for scoring and clinical interpretation by a board-certified sleep medicine physician within 7 days of study completion. The database sits behind a Cisco ASA 5520 firewall on a separate Microsoft SQL 2005 Server and will utilize whole database encryption technology using NetLib Encryptionizer (FIPS 140.2 compliant). All local information security practices will be implemented. Due to HIPAA and Institutional Review Board (IRB) guidelines, any personal identifying information transmitted from the participant to the research office needs to remain private and confidential. Data analysis will be performed under the direction of [name] (Senior Statistician) with assistance from the National Data and Statistical Center. **(Missing data):** To ensure data quality and minimize missing data several levels of data checks will be implemented. First, when data collectors enter data into the web based data entry program they will be notified which fields have been skipped. In general all fields, with the exception of some text fields, will have valid codes associated with them, so no true blank variables should exist in the database. Furthermore, when appropriate, skip patterns will exist for some variables, which can automatically populate variables that would then be considered "not applicable". The data entry program will also not allow an entry that isn't considered valid mostly through the use of drop down controls in which only valid answers are presented. Second, while data is being entered there will be a process for a data collector to run various data checks like logical errors (e.g. injury date occurring before birth date) or data inconsistencies (e. g. currently working, but hours of work past week = 0) can be programmed into the system to alert the data collector of variables that need attention. Above and beyond the notifications of errors and missingness that occurs while a data collector is entering data, all authorized people of the study can run real time reports that reflect not only missingness by variable, but missingness by person. Reasons for missingness have been

established in the TBIMS database and will be applied for this study (i.e., unknown, not applicable) and generated in missing data reports for discussion. As the primary hypotheses require complete data from each subject (STOPBang, ACG, Level 1 PSG, and Level 3 PSG) all efforts will be made to minimize missing data from these key variables. For example, a patient may need to repeat PSG if it was not adequately captured. Any reasons for missing data will be recorded for each patient for a global sensitivity analyses to examine the effect of missingness on the conclusions of the hypotheses tests. Missing data reports will be reviewed on a quarterly basis by staff at the NDSC as well as coordinators at each site. This study will be a multi-site, prospective observational study investigating the comparative effectiveness of sleep apnea screening (Aim 1) and diagnostic (Aim 2) measures. A total of 258 subjects will be recruited to allow for attrition and meet study goals. Initial analyses will be undertaken to inspect data for errors, inconsistencies, and incomplete information. This will include examining the distribution of the data (frequency tables, histograms, box-plots). Data anomalies that cannot be resolved will be examined by study staff for clarification and possible correction. During the verification process, we will correct any inaccuracies in data entry and track the changes in the data accordingly. Incomplete entries will also be rectified if the missing information is available. However, missing data are inevitable in any study. Given the novelty of this area, imputation methods for missing data will not be applied. Efforts to minimize missing data impacting analyses include 1) close monitoring of missing data in real time (missing data reports reviewed biweekly) and 2) repeat testing given the captive nature of the audience during inpatient rehabilitation. Serial attempt to capture data will be tracked and analyzed across key demographic and injury severity variables. We will also examine consent rates and attrition from time of consent to completion of diagnostic tests and illustrated with the use of the STARD diagram. Participants who drop-out vs. those who complete the study will be compared on the key demographic and injury severity variables (e.g., sex, race, severity measures) to determine if there are group differences. If differences are present, interpretations of all study results will be made in light of these differences. Data analysis will begin with a review of descriptive statistics for all major variables and all major subgroupings of variables in the data set.

Data analysis plan specific to each aim. The analytic methods designed *a priori* for each hypothesis are detailed below. Reporting of findings will strictly adhere to the requirements of the STARD guidelines.

Aim 1 (Hypothesis 1.1): *Sensitivity and specificity of actigraphy will be superior compared to clinical prediction rules (i.e., STOP-Bang) for determining risk of sleep apnea as diagnosed by Level 1 polysomnography in TBI patients undergoing inpatient rehabilitation.* **Justification of Assumptions/Power Estimate:** To test hypothesis 1.1, a paired-sample diagnostic analysis will be performed as the estimated sensitivities/specificities for STOPBang and ACG (each versus the reference gold standard, Level 1 PSG) will be estimated using the same sample of patients. Prevalence of sleep apnea (as determined by Level 1 PSG) is conservatively estimated to be 30% using investigators' published reports of 37-39% prevalence in acute rehabilitation TBI samples.¹⁻² A two-sided McNemar's test, assuming a significance level of $\alpha = 0.05$, will have at least 80% power to detect a difference in sensitivities of 20% between ACG and STOPBang if the total sample size is at least 237 patients. The power of the test will increase if the prevalence is higher than 30% (e.g., a prevalence of 35% would yield 87% power with 237 subjects and only require 203 subjects for 80% power). Furthermore, a sample size of 237 will have at least 80% power to detect a difference of 20% in sensitivities between actigraphy and STOP-Bang in detecting sleep apnea. **Analytic Plan:** The sensitivity (SE) and specificity (SP) of both STOPBang and ACG will be estimated using Level 1 PSG as the reference gold standard. As STOPBang and ACG are measured on an interval scale, and are not

dichotomous, pre-specified cut-points for each screening tool will be used to classify a subject as being at high risk for sleep apnea. We expect that STOPBang values > 5 and abnormal ACG total sleep time (< 5 hours with desaturation) will produce sufficiently high SEs with reasonable tradeoff in SP (noting that SE and SP are inversely related). Similarly, for Level 1 PSG, a diagnosis of sleep apnea will be made if $AHI \geq 5$. Cross-tabulations of STOPBang and ACG screening for high risk of sleep apnea (positive/negative) versus Level 1 PSG diagnosis (positive/negative) will be constructed and estimates of diagnostic accuracy (i.e., sensitivity, specificity, positive and negative predictive values, and diagnostic accuracy, ROC curves, AUC) will be estimated along with 95% confidence intervals. To address hypothesis 1.1, two-sided McNemar's tests will be used to compare the paired SEs and paired SPs between STOPBang and ACG assuming a significance level of $\alpha = 0.05$. All analyses will be performed using SAS v.9.4 (SAS Institute Inc., Cary, NC).

(Aim 2: Hypothesis 2.1): *Level 3 portable polysomnography with greater consumer accessibility will be equivalent (non-inferior) to the less accessible Level 1 polysomnography in determining presence of sleep apnea in TBI patients undergoing inpatient rehabilitation.* Justification of Assumptions/Power Estimate: To test hypothesis 2.1, the sensitivity (SE) and specificity (SP) of Level 3 PSG (compared to Level 1 PSG, the reference gold standard) will each be estimated and compared to fixed hypothesized rates of SE and SP considered sufficiently large enough to potentially obviate the need for Level 1 PSG. Based on a review of the literature and consensus among the investigators in this study, SE and SP no worse (non-inferior) to 90% and 60%, respectively, are considered sufficiently large enough. To test for non-inferiority of the SE to 90% and the SP to 60%, a non-inferiority threshold of $\Delta = 0.1$ is assumed for both measures. A sample size of at least 83 patients is necessary to achieve a minimum of 80% power to test the non-inferiority of the SE to 90% (assuming $\Delta = 0.1$ and $\alpha = 0.05$). A sample size of at least 153 patients is necessary for a minimum of 80% power to test the non-inferiority of the SP to 60% (assuming $\Delta = 0.1$ and $\alpha = 0.05$). Thus, a total of 153 subjects is required to sufficiently power both non-inferiority hypotheses. Analytic Plan: To test hypothesis 2.1, the sensitivity (SE) and specificity (SP) of Level 3 PSG (compared to Level 1 PSG, the reference gold standard) will each be estimated and compared to fixed hypothesized rates of SE and SP of 90% and 60%, respectively, considered sufficiently large enough. Level 1 PSG (reference) diagnosis of sleep apnea will be made based on $AHI \geq 5$. Level 3 PSG (test) diagnosis will be made based $AHI \geq 5$. A cross-tabulation of Level 3 PSG (positive/negative) versus Level 1 PSG (positive/negative) will be constructed and standard measures of diagnostic accuracy will be estimated along with 95% confidence intervals (i.e., sensitivity, specificity, positive and negative predictive values, and diagnostic accuracy). To test for non-inferiority of the SE to 90% and the SP to 60%, a non-inferiority threshold of 0.1 is assumed. If the lower bound on the 95% confidence interval for SE is strictly above 80% and the lower bound on the confidence interval for SP is strictly above 50% then non-inferiority of Level 3 PSG (compared to Level 3 PSG) can be established. All analyses will be performed using SAS v.9.4 (SAS Institute Inc., Cary, NC).

Exploratory Aim 1 (HTE analyses): While an analysis of heterogeneity of treatment effects does not apply to the current study design, an important question to answer is whether the diagnosis of sleep apnea can be impacted by the presence of post-traumatic amnesia (PTA). The confusion and behavioral dysregulation associated with PTA could potentially reduce the person's ability to tolerate the procedures. While the lead site has successfully obtained PSG with EEG with persons experiencing PTA, this was a single site study with a select subject population (veterans who primarily experienced blast-induced TBI). The current study will allow for an assessment of differences in diagnostic accuracy with persons who are currently experiencing PTA in comparison to those who have cleared PTA. PTA will be operationalized based on the criterion used by the TBIMS consortium (obtaining an Orientation Log or

Galveston Orientation Amnesia Test scores in target range or consistent, repeated demonstration of orientation in medical record review). Analytical Plan: To address exploratory aim 1 regarding the heterogeneity of the screening and diagnostic accuracy across relevant sub-groups, the methods detailed for the primary aims will be replicated for the subgroups of injury severity (GCS), cognitive status (PTA), motor confounds (spasticity and hemiparesis), and limb placement. As these are exploratory aims and the study is not powered to test for differences or non-inferiority within each sub-group, focus will be on comparing the effect size of proportions (Cohen's h) among the subgroups. Values for h of 0.2, 0.5, and 0.8 are typically considered to be small, medium, and large differences, respectively. All analyses will be performed using SAS v.9.4 (SAS Institute Inc., Cary, NC).

